7.9. Concomitant Therapy and eCOA Compliance

The summary and reporting of concomitant therapy and eCOA compliance has been described in the CPMP SAP Version 5. No additional covariates will be considered in the models of weekly rescue medication use.

Concomitant therapy will be reported separately for the 8 weeks of the double-blind period and for the entire 10-week study period.

7.10. Efficacy Analyses

7.10.1. Primary Outcome and Methodology

The analysis of the primary outcome has been described in the Study CPMP SAP Version 5, and it constrains baseline means to be equal between arms.

As noted in Section 5.1, endpoint

for the primary analysis is defined as 8 weeks post initial treatment administration.

Calculation of the weekly/biweekly time intervals used for analysis of weekly/biweekly mean scores from the eCOA device will follow the algorithm described in the Study CPMP SAP Section 6.12.1, except that the end of the final interval will be determined based on the last VAS collection date, or the last scheduled visit start date if VAS results are missing for the last scheduled visit.

Descriptive statistics of primary outcome variables by demographics, disposition, disease characteristics, and treatment administration may be summarized by ISA, in order to examine the population homogeneity assumption between ISAs.

7.10.3. Secondary Efficacy Analyses

Secondary efficacy analyses common to all ISAs within CPMP have been described in the CPMP SAP Version 5. Unless otherwise specified, the time point for secondary endpoint measurements is the same as that for the primary endpoint. Study NP05 will also consider the following secondary analyses.

The BPI-SF is a numeric rating scale that assesses the severity of pain (severity scale), its impact on daily functioning (interference scale), and other aspects of pain (for example, location of pain, relief from medications) in various disease states (Cleeland and Ryan 1994).

Table NP05.7.1 describes the pain scales and corresponding NRS used in a modified version of the BPI, validated for pain in diabetic polyneuropathy. Participants will rate their pain severity and how, during the past 24 hours, the pain has interfered with the activities described in the table.

Table NP05.7.1. Pain Scales and Corresponding NRS Used in a Modified Version of the BPI

Assessment	Topic	Numeric Rating Scale 0-10
4-item Pain severity	 Worst pain in last 24 hours 	0 = no pain
	• Least pain in the last 24 hours	10 = pain as bad as you can
	 Average pain 	imagine
	 Pain right now 	
7-item Pain interference	General Activity	0 = does not interfere
	 Mood 	10 = completely interferes
	 Walking ability 	
	 Normal work 	
	 Relations with others 	
	• Sleep	
	• Enjoyment of life	

Abbreviations: BPI = Brief Pain Inventory; NRS = numeric rating scale.

A Bayesian longitudinal MMRM analysis will be performed to evaluate the change from baseline to each postbaseline visit up to Week 8 for the mean pain interference scale and the mean pain severity scale. The model will utilize the cLDA model so that a common mean is estimated at the baseline. More details on this approach are provided in Study CPMP SAP Version 5.

Additional Bayesian MMRM analyses will be used to analyze the change from baseline to each postbaseline visit for:

- individual pain interference, and
- individual pain severity scales.

Table NP05.7.2 describes information included in the model.

Table NP05.7.2. Categorical Effects and Continuous Covariates Used in Bayesian MMRM analyses

Categorical effects	 the interaction of treatment and visit (constrained to estimate a common mean at baseline across treatments) average baseline pain severity category (baseline NRS <7, baseline NRS ≥7)
	 pooled investigative site
Continuous covariates	• none

Abbreviation: NRS = numeric rating scale.

Other Secondary Analysis

The proportion of participants in each treatment group meeting prespecified binary efficacy outcomes will be calculated for each postbaseline time point and will be used to compare treatment groups. The prespecified binary efficacy outcomes include the proportion of participants with a reduction of at least 30%, 50%, and 70% from baseline as measured by the BPI:

- mean pain interference score
- mean pain severity score
- individual interference scores, and
- individual severity scores.

A Bayesian pseudo-likelihood-based categorical repeated measures model will be used to estimate the proportion of participants in each treatment group meeting the prespecified threshold for each postbaseline time interval up to Week 8. These estimates will be used to compare treatment groups. More details on this approach are provided in Study CPMP SAP Version 5.

In addition, time to first treatment response from baseline based on the prespecified binary thresholds above will be assessed. Analyses will be conducted according to the time to event analyses specified in the CPMP SAP Version 5.

7.11. Pharmacokinetic/Pharmacodynamic Methods

The plasma concentrations for LY3857210 will be reported graphically and summarized descriptively across the study visits.

Exploratory model-based analyses may be conducted to assess the relationship of LY3857210 plasma concentrations to efficacy and/or safety outcomes.

Additional analyses may be conducted, as needed.

Data from this study may be pooled with data from other studies.

7.12. Safety Analyses

The general analysis of safety has been described in Study CPMP SAP Version 5. However, additional ISA-specific safety considerations are described in the sections below.

7.12.1. Extent of Exposure

Duration of exposure (defined as time since first dose of study treatment to last dose of study treatment in days) to study drug will be summarized by treatment group using descriptive statistics; the summary will also include the total exposure in patient years.

Duration of exposure (days):

Date of last dose during the double-blind treatment period – Date of first dose for the treatment period $+\ 1$

Total exposure in patient years will be calculated as follows:

Summary of duration (days) of exposures for all patients in the treatment group / 365.25.

7.12.2. Adverse Events

The general analysis of AEs has been described in Study CPMP SAP Version 5.

This ISA will report TEAEs separately for the entire 8-week double-blind period, the 2-week posttreatment period, and the entire 10-week study. For TEAEs in the double-blind period, the baseline will be prior to first dose date.

A PTEAE is defined as an event that first occurs or worsens in severity after double-blind treatment phase (after Visit 7) and on or before study discontinuation. This ISA will report PTEAEs for the posttreatment period, as they are important for assessing withdrawal or abuse

liability potential. The MedDRA LLT will be used in the posttreatment-emergent computation. The maximum severity for each LLT during the double-blind treatment period (Visits 3 through 7) will be used as a reference.

The baseline of PTEAE is from the first dosing date to Visit 7. The posttreatment phase will be included as postbaseline for this analysis. While unusual, it is possible to have a missing severity for events.

PTEAEs will be determined by

comparing with treatment period.

PTEAEs will be summarized by PT and by PT within System Organ Class in participants who received LY3857210.

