4.1. Overall Design

Master Protocol CPMP describes the overall study design and study design rationale. This section describes visits and overall procedures unique to ISA NP05 for LY3857210 in addition to the procedures outlined in CPMP and CPMP(3).

Double-blind treatment period (Visits 3 through 7)

Each visit is an outpatient visit.

At Visit 3,

- participants are randomly assigned to LY3857210 or placebo
- the site completes the NP05 baseline procedures and sample collection (excluding PK) prior to study intervention
- the site collects participants' vitals predose
- participants receive their oral study intervention
- the site completes PK sample collection, and
- the site instructs participants to continue with study restrictions and NRS diary entries before their visit discharge.

At Visits 4 through 7,

- the site reviews available safety data and sample collection
- participants continue oral study intervention (not applicable for Visit 7) and bring all study intervention bottles to each visit
- the site completes all sample collection and safety monitoring noted in the SoAs, and
- the site instructs participants to continue with study restrictions, NRS diary entries, and wearing of CCI before their visit discharge.

Double-blind post-treatment follow-up period (Visit 801)

- Participants must complete 1 post-treatment follow-up visit for safety and efficacy assessment at Visit 801 according to the SoA
- the site schedules Visit 801 approximately 2 weeks after Visit 7 or ED Visit, and
- at Visit 801, participants return the devices CCI

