	7.12.1.	Adverse Events	
	7.12.3.	Deaths, Other Serious Adverse Events, and Other Notable	
	_	Adverse Events	15

Page	3
------	---

	7.12.4.	Neurological Exam	15
	7.12.5.	Clinical Laboratory Evaluation	15
	7.12.6.	Vital Signs and Other Physical Findings	16
	7.12.7.	Electrocardiograms	16
	7.12.8.	Suicidal Ideation or Behavior	16
7	.13. Sub	ogroup Analyses	16
7	.14. Pro	tocol Deviations	16
7	.15. Inte	erim Analyses and Data Monitoring	16
7	.16. Pla	nned Exploratory Analyses	17
7	.17. Tot	ality of Evidence for Efficacy	17
7	.18. Tot	ality of Evidence for Safety	18
7	.19. Anı	nual Report Analyses	18
7	.20. Clii	nical Trial Registry Analyses	19
8.	Unblin	nding Plan	20
9.	Refere	nces	21

3. Abbreviations and Definitions

[figure not shown]
Term	Definition
AE	adverse event
ALT	alanine aminotransferase
API	average pain intensity
AST	aspartate aminotransferase
BPI-SF	Brief Pain Inventory-Short Form
вма	Bayesian model averaging
cLDA	constrained longitudinal data analysis
compliance	Adherence to all study-related, good clinical practice (GCP), and applicable regulatory requirements.
CPMP	H0P-MC-CPMP
CTR	Clinical Trial Registry
ECG	electrocardiogram
eCOA	Electronic Clinical Outcome Assessment
eGFR	estimated glomerular filtration rate
enroll	The act of assigning a participant to a treatment. Participants who are enrolled in the study are those who have been assigned to a treatment.
FDA	United States Food and Drug Administration
FMQ	FDA Medical Query
GFR	glomerular filtration rate
ISA	intervention-specific appendix
LLT	Lowest Level Term
LY	LY3857210
MedDRA	Medical Dictionary for Regulatory Activities
MMRM	mixed-effect model for repeated measures
NP05	H0P-MC-NP05
NRS	numeric rating scale

Term	Definition
participant	Equivalent to CDISC term "subject": an individual who participates in a clinical trial, either as recipient of an investigational medicinal product or as a control
PDEP	preliminary data entry period
PK/PD	pharmacokinetics/pharmacodynamics
CCI	
РТ	Preferred Term
PTEAE	posttreatment-emergent adverse event
QTcF	Fridericia's corrected QT interval
SAP	statistical analysis plan
SMQ	standardized MedDRA query
TEAE	Treatment-emergent adverse event: An untoward medical occurrence that emerges during a defined treatment period, having been absent pretreatment, or worsens relative to the pretreatment state, and does not necessarily have to have a causal relationship with this treatment.
ТоЕ	totality of evidence
ULN	upper limit of normal
VAS	visual analog scale

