7.12.3. Deaths, Other Serious Adverse Events, and Other Notable Adverse Events

TEAEs by PT will be reported.

The general summary of AEs is described in Study CPMP SAP Version 5. Other AEs include

- abuse liability and withdrawal potential following the most recent Lilly Guidance for Assessment of Abuse Potential during Clinical Development, and
- seizures FMQ both narrow and broad terms will be analyzed.

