7.20. Clinical Trial Registry Analyses

Additional analyses will be performed for the purpose of fulfilling the CTR requirements.

Analyses provided for the CTR requirements include the following:

- Summary of AEs, provided as a dataset that will be converted to an XML file. Both "Serious" AEs and "Other" AEs are summarized by treatment group and by MedDRA PT.
- A serious AE is an AE that is considered "Serious" whether or not it is a treatment emergent.
- An AE is considered in the "Other" category if it is both a TEAE and is not serious. For each "Serious" AE and "Other" AE, for each term and treatment group, the following are provided:
 - o the number of participants at risk of an event
 - o the number of participants who experienced each event term, and
 - o the number of events experienced.
- Consistent with www.ClinicalTrials.gov requirements, "Other" AEs that occur in fewer than 5% of participants in every treatment group may not be included if a 5% threshold is chosen (5% is the minimum threshold).
- AE reporting is consistent with other document disclosures (for example, the Clinical Study Report and manuscripts).

8. Unblinding Plan

The general unblinding plan is described in Study CPMP SAP Version 5 and in Study CPMP Blinding and Unblinding Plan Version 2. Unblinding considerations specific to Study NP05 are provided below.

PK/PD analysis planning

A limited number of prespecified individuals who are not part of the blinded study team and do not have direct site contact, data entry, or data validation responsibilities, may receive access to unblinded data, prior to an interim or final database lock, to initiate the PK and/or PK/PD model development processes. This will be described in the unblinding plan. Information that may unblind the study during the analyses will not be reported to study sites or blinded study team until the study has been unblinded.

9. References

Signature Page for VV-CLIN-093328 v1.0

Approval F	PPD
•	Statistician
	27-Jun-2023 15:48:24 GMT+0000

Signature Page for VV-CLIN-093328 v1.0

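### The PTEAE table meant to assess withdrawal or abuse liability is restricted to LY3857210 recipients, so it has no placebo comparison

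*SAP*

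**What the plan says.** SAP 7.12.2 gives the purpose of the PTEAE analysis: "This ISA will report PTEAEs for the posttreatment period, as they are important for assessing withdrawal or abuse" liability potential. A PTEAE is an event that first occurs, or becomes more severe, after the double-blind treatment phase. The comparison is made within each participant: "The maximum severity for each LLT during the double-blind treatment period (Visits 3 through 7) will be used as a reference".

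The section then fixes who is in the table: "PTEAEs will be summarized by PT and by PT within System Organ Class in participants who received LY3857210". The extracted text breaks just before this sentence, but the sentence itself is complete.

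Three other places in the SAP touch the same ground:

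- SAP 7.12.2 also says: "This ISA will report TEAEs separately for the entire 8-week double-blind period, the 2-week posttreatment period, and the entire 10-week study". No arm restriction is stated. The section gives a baseline for double-blind-period TEAEs (before first dose) but none for the posttreatment TEAE report.
- SAP 7.12.3 lists "abuse liability and withdrawal potential following the most recent Lilly Guidance for Assessment of Abuse Potential during Clinical Development" and names no comparator.
- SAP 7.20 describes a registry summary by treatment group. It counts a serious event "whether or not it is a treatment emergent" and is not specific to the posttreatment period.

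Protocol 4.1 describes the follow-up to Visit 801 as double-blind and requires that visit of participants without regard to arm. Protocol 1.3 schedules AE collection at Visit 801. Protocol 6.8.2 applies medication restrictions up to Visit 801 to everyone randomised to this study.

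**The concern.** A withdrawal effect is an excess of events after stopping the active drug over what would be seen after stopping placebo. Comparing each participant with their own treatment period identifies events that are new or worse, but it does not remove the background rate. Over two weeks, intercurrent illness, return of underlying symptoms, and reporting prompted by the follow-up visit can all produce PTEAEs in people who never took LY3857210.

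A table limited to LY3857210 recipients cannot distinguish the two sources. A raw rate could be read as a withdrawal signal when it is only background, or dismissed as background when it is an excess. The trial has a concurrent, randomised, blinded control for exactly this period, and the table as written does not use it.

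**Working it through.** **1. Is the restriction deliberate wording or shorthand?** Where the SAP wants both arms, it says that the summary is by treatment group: compliance (7.8), exposure (7.12.1) and registry AEs (7.20). The PTEAE sentence instead names the LY3857210 recipients. On its face it is a one-arm table.

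**2. Does another visible output give the same comparison?**

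| Output | Placebo shown? | Reference | Period |
|---|---|---|---|
| PTEAE table (7.12.2) | No | On-treatment maximum severity by LLT | Posttreatment |
| Posttreatment TEAE report (7.12.2) | Not restricted | Not stated for this period | Posttreatment |
| Abuse/withdrawal item (7.12.3) | Not stated | Not stated | Not stated |
| Registry AEs (7.20) | Yes | Serious events: emergence not required; other events: TEAE | Not specific to posttreatment |

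The posttreatment TEAE report comes closest. The general TEAE definition in SAP Section 3 refers to an event "having been absent pretreatment, or worsens relative to the pretreatment state". If that reference is used, a symptom that was present before treatment, improved on treatment and returned to its earlier level after stopping would be a PTEAE but not a TEAE. If the on-treatment reference is used instead, the two outputs may largely coincide. The SAP does not say which applies.

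**3. What can a one-arm rate show?** The documents give no figure for this analysis, so there is nothing to reproduce, and what follows is illustration. The Protocol synopsis gives up to about 125 randomised and 20% dropout, so 125 × 0.80 = 100. The allocation ratio is not in the available text; assume 1:1, giving 50 per arm. Suppose 5/50 (10%) on LY3857210 have a PTEAE; the exact 95% interval is 3.3% to 21.8%. The difference depends entirely on the column that is not planned (Newcombe limits, formula in step 4):

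- placebo 0/50: +10 points (0.9 to 21.4)
- placebo 5/50: 0 points (-12.7 to +12.7)

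The same LY3857210 count fits either picture.

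**4. How precise would the added column be?** Assumptions: equal PTEAE rates p of 10% or 5% in both arms, and allocation of 1:1 or 2:1. Arm sizes (LY3857210/placebo) are 62/62 or 83/42 from 125 (rounded), and 50/50 or 67/33 from 100. Early leavers may also attend Visit 801, so the denominators should lie between these cases.

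With Wilson limits (l₁, u₁) for LY3857210 and (l₂, u₂) for placebo, the Newcombe 95% limits for p₁ − p₂ are

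lower = (p₁ − p₂) − √[(p₁ − l₁)² + (u₂ − p₂)²]

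upper = (p₁ − p₂) + √[(u₁ − p₁)² + (p₂ − l₂)²]

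Example, p = 10% and 50/50: Wilson limits are 4.35% and 21.36% in each arm, so the half-width is √(5.65² + 11.36²) = 12.7 points.

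| Arms | Limits at 10% (points) | Placebo with event (n × p) | Limits at 5% (points) | Placebo with event (n × p) |
|---|---|---|---|---|
| 62/62 | -11.3 to +11.3 | 6.2 | -9.1 to +9.1 | 3.1 |
| 83/42 | -13.5 to +10.2 | 4.2 | -11.5 to +7.9 | 2.1 |
| 50/50 | -12.7 to +12.7 | 5.0 | -10.4 to +10.4 | 2.5 |
| 67/33 | -15.6 to +11.4 | 3.3 | -13.5 to +8.9 | 1.7 |

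For a single preferred term at an assumed 2%, the chance of no placebo event is 0.98ⁿ: 29% (n = 62), 36% (50), 43% (42) and 51% (33). The column would be most useful for the overall PTEAE rate and the commoner terms.

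**The case against.** The best counter-argument is that a placebo view may already exist. The posttreatment TEAE report covers the same two weeks with no arm restriction, and general AE analyses are deferred to CPMP SAP Version 5. The abuse and withdrawal assessment follows a sponsor guidance. Neither of those two sources is available here, and either could contain a by-arm display.

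Much of this stands. A reader might infer that all posttreatment safety data lack a placebo comparison, and the documents do not support that. A reader might also infer that every other AE output necessarily uses a different reference or period. That goes too far as well: the pre-dose baseline in 7.12.2 is stated only for the double-blind period, so the reference for posttreatment TEAEs is open. That report may supply part of the placebo background.

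What does not follow is that the PTEAE sentence is harmless. It is specific to this study, and no visible text applies the PTEAE definition to placebo. If an unseen document does, the sentence in 7.12.2 still needs to be reconciled with it.

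It can also be said that the placebo column would be too sparse to matter, and that it could be produced later because the events are recorded anyway. The sparsity is real, above all for single terms. It argues for description without testing, not for leaving out the control. That the column could be added later keeps the consequence small, but specifying it before unblinding is cleaner than adding it after the LY3857210 rates are known.

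**Conclusion.** The concern holds for the PTEAE table only. As written, the table has no placebo comparison, and by itself it cannot serve its stated purpose of assessing withdrawal or abuse liability. This rests on an explicit sentence, not on a missing detail.

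The consequence is limited: one descriptive safety summary in a proof-of-concept trial, with no effect on the primary analysis. A placebo column would give a rough background rate, not a precise contrast. The limits of about 8 to 16 points from zero depend on assumed rates and allocation. The conclusion that the table lacks a control does not depend on them. It is subject to what CPMP SAP Version 5 and the sponsor guidance may add.

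**What to change.** Change the sentence in SAP 7.12.2 so that PTEAEs are summarised by PT, and by PT within SOC, for each treatment group (LY3857210 and placebo). Add an overall row for participants with any PTEAE, and state that the comparison is descriptive with no testing.

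The cost is one amended sentence, one extra column and one extra row. No new data are needed, because AEs are already collected at Visit 801 without regard to arm. The small downside is a sparse placebo column that could be over-read, so the text or a table footnote should say that it is imprecise.

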7.12.3. Deaths, Other Serious Adverse Events, and Other Notable Adverse Events

TEAEs by PT will be reported.

The general summary of AEs is described in Study CPMP SAP Version 5. Other AEs include

- abuse liability and withdrawal potential following the most recent Lilly Guidance for Assessment of Abuse Potential during Clinical Development, and
- seizures FMQ both narrow and broad terms will be analyzed.

7.12.4. Neurological Exam

In this ISA, neurological exam results will be reported for the entire 10-week study period. Study NP05 will consider the following analyses for the Neurological Exam, which evaluates 6 items and will be summarized by normal/abnormal percentage by item. In addition, we will summarize shift tables for each item in the Neurological Exam.

7.12.5. Clinical Laboratory Evaluation

The general analysis of laboratory parameters is described in Study CPMP SAP Version 5.

In this ISA, laboratory results will be reported for the entire 10-week study period. Study NP05 will also consider the following analyses of lab analytes used to assess renal function. The planned summaries for these analytes are the same as those that have been described in Study CPMP SAP Version 5. However, the reporting of these analytes will be separate from the general analysis of laboratory parameters.

- Renal data analyses:
 - o serum creatinine (change from baseline in mg/dL)
 - o eGFR; Chronic Kidney Disease Epidemiology Collaboration (algorithm using serum creatinine) Algorithm: Provided by central laboratory

- for eGFR calculation, we will summarize shift tables of eGFR changes for baseline versus postbaseline by minimum, maximum, and last observed eGFR result:
 - Category 1: Normal or increase in GFR (≥90 mL/min/1.73 m²)
 - Category 2: Mild reduction in GFR (60 to 89 mL/min/1.73 m²)
 - Category 3a: Moderate (a) reduction in GFR (45 to 59 mL/min/1.73 m²)
 - Category 3b: Moderate (b) reduction in GFR (30 to 44 mL/min/1.73 m²)
 - Category 4: Severe reduction in GFR (15 to 29 mL/min/1.73 m²)
 - Category 5: Kidney failure (GFR <15 mL/min/1.73 m² or dialysis).

Abnormal eGFR is specified below and will be summarized in the laboratory summary tables.

- Abnormal low: <90 mL/min/1.73m²
- Abnormal high: As specified by central laboratory.

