7.1. General Considerations

The estimand for the primary clinical question of interest has been described in the CPMP SAP Version 5

Unless otherwise specified, efficacy and safety analyses will be conducted for the 8-week double-blind period and separately for the entire 10-week study period.

Other general considerations for analyses are described in the CPMP SAP Version 5.

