7.12.6. Vital Signs and Other Physical Findings

The analysis of vital sign parameters is described in Study CPMP SAP Version 5.

Vital signs will be reported separately for the 8-week treatment period and the entire 10-week study period.

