7.12.7. Electrocardiograms

The analysis of ECG parameters is described in Study CPMP SAP Version 5. ECGs will be reported separately for the 8-week treatment period and the entire 10-week study period.

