7.12.8. Suicidal Ideation or Behavior

Reporting of suicidal ideation/behavior through the Columbia Suicide-Severity Rating Scale has been described in Study CPMP SAP Version 5. Suicidal ideation/behavior will be reported separately for the 8-week treatment period and the entire 10-week study period.

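### Laboratory and neurological-exam results are given only a 10-week window, so the 'last observed' eGFR shift becomes an off-drug value for anyone with a Visit 801 result

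*SAP*

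**What the plan says.** The SAP's general rule in section 7.1 is: "Unless otherwise specified, efficacy and safety analyses will be conducted for the 8-week double-blind period and separately for the entire 10-week study period".

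Three safety sections repeat that rule:
- 7.12.6: "Vital signs will be reported separately for the 8-week treatment period and the entire 10-week study period".
- 7.12.7: "ECGs will be reported separately for the 8-week treatment period and the entire 10-week study period".
- 7.12.8: "Suicidal ideation/behavior will be reported separately for the 8-week treatment period and the entire 10-week study period".

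Two sections do not:
- 7.12.4: "In this ISA, neurological exam results will be reported for the entire 10-week study period".
- 7.12.5: "In this ISA, laboratory results will be reported for the entire 10-week study period".

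Section 7.12.5 also plans eGFR shift tables of "baseline versus postbaseline by minimum, maximum, and last observed eGFR result", with no limit to the treatment period. Section 7.12.4 plans shift tables for each exam item but does not say which postbaseline value they use. Section 7.18 lists treatment-emergent eGFR shifts and a treatment-emergent shift on the overall neurologic assessment among its key safety events, and gives no window for either.

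**The concern.** Visit 801 is the off-treatment follow-up, scheduled about 2 weeks after Visit 7 or early discontinuation (Protocol 4.1). A table that takes the last value over 10 weeks describes participants after the drug has been stopped. If the drug changes creatinine or eGFR and the change reverses within about two weeks, the last-value table will tend to show nothing. A change first seen at Visit 801 would enter the same table with no sign that it arose after treatment.

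The neurological exam has a similar exposure if its shift tables use a last or worst value. That exam matters here because Protocol 2.3.1 presents it as one of the safeguards adopted after convulsions were seen in animal studies. Any ambiguity about the window can also carry into the totality-of-evidence assessment in 7.18.

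**Working it through.** The plan states no figure that tests this point, so there is none to reproduce. The check sets the sections against the schedule and then adds some simple arithmetic.

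**Step 1. Windows named in the SAP.**

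| Section | Content | 8-week | 10-week |
|---|---|---|---|
| 7.1 | Default, unless otherwise specified | yes | yes |
| 7.12.2 | Adverse events (also the 2-week posttreatment period) | yes | yes |
| 7.12.4 | Neurological exam | not named | yes |
| 7.12.5 | Laboratory, including renal tables | not named | yes |
| 7.12.6 to 7.12.8 | Vital signs, ECG, suicidality | yes | yes |

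**Step 2. What is collected off drug (Protocol 1.3, NP05 schedule).**
- Chemistry, hematology and lipids: V4, V5, V6, V7 and V801.
- Urinalysis: V7 and V801.
- Neurological assessment: V3 to V7, ED and V801.
- HbA1c: V3, V7 and ED, but not V801.

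One of the five scheduled postbaseline chemistry visits is off drug (1/5 = 20%), and it is the last one. The two windows coincide for HbA1c. The master protocol and the disease-state addendum have their own schedules, which are not available here.

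**Step 3. How many last values are off drug.** The protocol synopsis gives up to about 125 randomized and an assumed 20% dropout before the end of double-blind treatment. Completers: 125 × (1 − 0.20) = 100, or 80%. If all of them attend V801, about 100 last-observed eGFR values are off drug. The number falls if completers miss V801 and rises if early discontinuers attend it.

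**Step 4. What the last-value table can lose.** Take participants with an eGFR shift at V7. Let a be the proportion with a V801 result and r the proportion of shifts reversed by then. The share still visible as last observed is 1 − a × r. Both inputs are assumptions.

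| | r = 0 | r = 0.5 | r = 1 |
|---|---|---|---|
| a = 0.8 | 100% | 60% | 20% |
| a = 0.9 | 100% | 55% | 10% |
| a = 1.0 | 100% | 50% | 0% |

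A table that ends at V7 keeps 100% in every cell.

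**Step 5. Minimum and maximum.** The minimum over V4 to V801 cannot exceed the minimum over V4 to V7, so a recovered V801 value never erases an on-drug low. The statistic changes only when V801 is lower still. The same holds for the maximum with the sign reversed. These two tables mix the periods but do not lose the on-drug extreme.

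**Step 6. A worst-value neurological table, if that is what is planned.** Assume an independent per-exam chance p of an abnormality. The chance of at least one abnormality over k exams is 1 − (1 − p)^k.

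| p | k = 4 (V4 to V7) | k = 5 (adding V801) |
|---|---|---|
| 0.01 | 3.9% | 4.9% |
| 0.02 | 7.8% | 9.6% |
| 0.05 | 18.6% | 22.6% |
| 0.10 | 34.4% | 41.0% |

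The fifth exam adds about 1 to 7 percentage points. If the abnormalities are unrelated to drug, the addition is expected equally in both arms. It is noise, not evidence of a misattributed effect, and independence between repeat exams is doubtful for persistent findings.

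**The case against.** The strongest case on the other side has four parts.

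- **The word 'only' does not appear.** Sections 7.12.4 and 7.12.5 do not exclude an 8-week analysis, so the 7.1 default might still apply. That is possible, but three neighbouring sections restate both windows, which makes 10 weeks alone the natural reading. On either reading the text needs reconciling, because a programmer cannot tell which tables to produce.
- **Other output may separate the periods.** A reader might infer that on-drug and off-drug results cannot be told apart anywhere. The documents do not support that. Section 7.12.5 leaves the general laboratory summaries to CPMP SAP Version 5, which is not available here, and by-visit summaries there would keep V4 to V7 apart from V801. They would not correct the last-observed shift table.
- **Convulsion and withdrawal are handled elsewhere.** A reader might infer that a seizure or withdrawal signal would be blurred. It would not be. Convulsion is an adverse event of special interest and is analysed through the seizures FMQ. Section 7.12.2 reports events by period and defines posttreatment-emergent events against the maximum severity on treatment. This part stands in full.
- **A whole-study table is legitimate and does not claim to be on-treatment.** That is fair: a 10-week table labelled as such does not count off-drug findings as on-drug ones. The gap is that no on-treatment counterpart is named.

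**Conclusion.** The point holds in a limited form. As written, 7.12.4 and 7.12.5 depart from the SAP's own default. The clear consequence is in one place: the last-observed eGFR shift is an off-drug value for every participant with a V801 chemistry result. The figure of about 100 of 125 rests on the planned sample, the planned dropout and full V801 attendance among completers. It is an expectation, not a floor.

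How much is lost depends on reversibility, which the documents do not give. The table loses nothing if no shifts reverse, 40% to 50% of V7 shifts if half reverse, and 80% to 100% if all reverse, with 80% to 100% attendance.

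The exposure of the neurological shift tables is conditional, because their statistic is not stated. The minimum and maximum eGFR tables are mixed, not replaced, and HbA1c is untouched under the NP05 schedule. It would go too far to say that all laboratory safety output is compromised. Adverse-event reporting, the primary analysis and the sample size are not affected. This is a cheap improvement to safety description that should be made.

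**What to change.** - In 7.12.4 and 7.12.5, report results for the 8-week treatment period and separately for the 10-week period, as 7.1 does. Include the separate renal tables.
- Take minimum, maximum and last-observed eGFR within each period, so that the 8-week last value is the last one in the treatment period.
- In 7.12.4, name the postbaseline value used for the neurological shift tables (by visit, last or worst).
- In 7.18, apply the 8-week window to the treatment-emergent eGFR and neurological shift events.

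The cost is a few sentences in three SAP sections and a second run of existing table programs. The downside is more table output. No new data are needed.
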